4 RESEARCH QUESTION/AIM(S)

The purpose of the present study is to test whether theory and evidence-based alternative communication formats, targeting message specificity and previously identified psychosocial predictors of adherence, could improve the behavioural impact of existing alert systems, compared to the official messages sent in association with the UK AQIs.

Research questions

Primary questions:

1) What is the main effect of using behaviourally enhanced messages, compared to the currently used DAQI messages, to present the health advice associated with air quality notifications for a hypothetical high air pollution scenario on adherence intentions?

Prediction:

A) The behaviourally enhanced messages will lead to stronger intentions to adhere to recommendations.

2) What is the main effect of using a behaviourally enhanced message, compared to the currently used DAQI messages, to present the health advice associated with air quality notifications on actual behaviour changes at four weeks?

Prediction:

A) The enhanced messages will lead to greater behaviour changes.

3) In case of a real alert being issued during the study period, how do the different messages affect actual behaviour change?

Prediction:

A) The enhanced messages will lead to greater behaviour change.

Secondary questions:

4) If there is a format effect, which variables mediate the relationship between the information format and behaviour change?

5) Which factors are associated with greater behaviour change across all groups?

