	Actual Behaviour change ^c	In response to receiving the air quality alert: 
 - I reduced length or level of my physical activity outdoors - I changed my travel route - I changed my exercise location - I changed the time when I travelled - I changed the time when I exercised outdoors - If you answered no, please report the reasons [text box].
	Medication adherence ^c	If you have lung problems: 
 - I used my preventer inhaler daily - I carried my reliever inhaler with me when going outdoors. - If you answered no, please report the reasons [text box].
Final Online Questionnaire – at 4 weeks	Behaviour change at 4 weeks ^b	- In the past 4 weeks, how often have you taken action to reduce exposure to air pollution, I response to hearing or reading an air quality forecast?
	Physical activity ^d	- To stay healthy, the NHS recommends at least 150 minutes of moderate physical activity (e.g. cycling, fast walking, swimming) every week (e.g. 30 minutes 5 days a week). Based on this, how physically active were you in the last week? ^e
	Action planning	
 - In the last 4 weeks, to reduce your exposure to air pollution, have you considered making permanent changes to your daily travel route or exercise place and time?^c - In the last 4 weeks, how often have you checked air quality information before doing physical activity outdoors?^b
	Worry ^a	Adapted from Witte et al. (34) 
 - The information received through the CityAir app made me worry about the possibility of suffering health effects from exposure to air pollution

	- The information received through the CityAir app made me nervous and tense about the possibility of suffering health effects from exposure to air pollution
Severity ^a	Adapted from Witte et al. (34)
	- Air pollution is a severe threat to my health
Conditional susceptibility ^f	- How likely do you think you are to suffer from health effects due to air pollution if you do not take any action to reduce exposure? - How likely do you think people of your same age and sex are to suffer from health effects due to air pollution if they do not take any action to reduce exposure?
Response efficacy ^a	Adapted from Witte et al. (34)
	- Following the health advice received through the CityAir app is effective in protecting me from exposure to air pollution

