6. STATISTICAL ANALYSES

6.1 Quantitative data

ANCOVAs will be performed for all the intentions measures in relation to the high air pollution hypothetical scenario, adjusting for baseline measures collected about one month earlier (target population and intervention/control group entered as fixed factors). Both main and interaction effects will be tested. ANCOVAs will also be performed for the actual behaviour change at 4 weeks (with the intervention/control group entered as fixed factor). These latter analyses will also be ran in the subgroups of healthy and at-risk participants. Chi square tests will be performed to analyse differences in proportion of self-reported actual behaviour change between groups, in relation to a real moderate air pollution episode. A two-way MANOVA (1000 bootstraps) will test whether there are differences between groups (both main effects and interactions) in perceived susceptibility, worry, severity, perceived response efficacy, perception of time, self-efficacy, trust, clarity, credibility and perceived informed choice measures. Multiple linear regressions will be used to assess the associations between main predictor variables and self-reported behaviour change at 4 weeks. Mediations effects of predictor variables on significant behavioural changes will be tested using PROCESS macro (38).

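### Primary question 3 has five behaviour items but no named outcome or multiplicity rule: if each is tested at 5%, the chance of a false difference is about 23% under independence

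*Combined protocol and SAP*

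**What the plan says.** Section 4 lists three primary questions. The third is "In case of a real alert being issued during the study period, how do the different messages affect actual behaviour change", with the directional prediction "The enhanced messages will lead to greater behaviour change". It names no item, score or composite.

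The outcome is defined only in section 5.6, Table 4, under the questionnaires sent in the alert period. The measure of actual behaviour change has five statements. The first is "I reduced length or level of my physical activity outdoors". The other four concern a different route, a different place of exercise ("I changed my exercise location"), a different time of travel and a different time of outdoor exercise. The table notes allow three answers to each: yes, no or not sure. Medication adherence is a separate row of the table, for people with lung problems only.

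The analysis is one sentence of section 6.1: "Chi square tests will be performed to analyse differences in proportion of self-reported actual behaviour change between groups". That sentence confines the tests to a real episode at the moderate level. The document gives no scoring rule for the five items, no treatment of *not sure*, no criterion for success and no adjustment for multiple tests. An alpha of 0.05 appears only in the sample size paragraph of section 5.3, where it is not divided among outcomes.

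**The concern.** A primary question with a directional prediction should have one outcome, or a rule for combining several. Here there are five candidates, and nothing prevents one significant item from being reported as support for the prediction. The 5% level in section 5.3 then does not describe the error rate of the question as a whole.

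This matters because the trial aims to improve the behavioural effect of alerts, and these items are its only alert-specific measure of the five named behaviours. There may also be a knock-on effect. Section 6.1 limits the mediation analysis to behavioural changes that reach significance. If the alert items are among those meant (the plan does not say), a false positive item would carry through to a mediation claim.

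**Working it through.** The plan states no overall error rate for question 3, so there is no figure of its own to reproduce.

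**Inputs**
- Number of items: 5 (section 5.6, Table 4).
- Level per test: 0.05, two-sided. The 0.05 is carried over from section 5.3. Section 6.1 gives no level and the document does not state sidedness, so this is an assumption.
- Answers reduced to yes against all others, so that a difference has a direction. This is also an assumption.
- Simulation only: 240 × 0.8 = 192 participants after the 20% dropout allowance, which is 96 per arm at an assumed 1:1 ratio, and 48 per arm as a smaller case. Each item has an assumed yes rate of 36% in both arms; section 1.1.5 gives 36% as the median adherence for reducing or rescheduling outdoor activities.

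**Step 1. Independent items, either direction.** 1 − 0.95^5 = 1 − 0.7738 = 0.2262, or 22.6%.

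**Step 2. Any dependence, either direction.** The sum of the five error rates is an upper bound: 5 × 0.05 = 0.25, or 25%.

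**Step 3. Predicted direction only.** Each two-sided 5% test gives a false result favouring the enhanced messages 2.5% of the time. For five independent items, 1 − 0.975^5 = 1 − 0.8811 = 0.1189, or 11.9%. The bound under any dependence is 5 × 0.025 = 12.5%. One test would give 2.5%.

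**Step 4. Positively correlated items.** Five binary items were simulated from equally correlated latent normal variables with no difference between arms, 20,000 replicates per setting. The simulation error on a rate near 20% is about √(0.2 × 0.8 / 20,000) = 0.3 percentage points. Each cell gives 96 per arm / 48 per arm.

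| Latent correlation | Any item at 0.05, either direction | Any item at 0.05, predicted direction | Any item at 0.01, either direction |
|---|---|---|---|
| 0 | 22.3% / 23.2% | 11.6% / 11.8% | 4.9% / 4.8% |
| 0.3 | 21.9% / 21.7% | 11.1% / 11.0% | 4.9% / 4.7% |
| 0.5 | 20.1% / 20.3% | 10.1% / 10.1% | 4.7% / 4.7% |
| 0.7 | 18.1% / 17.9% | 9.1% / 9.0% | 4.2% / 4.0% |
| 0.9 | 15.0% / 14.3% | 7.5% / 7.1% | 3.6% / 3.3% |

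The first row agrees with steps 1 and 3. Correlation reduces the inflation, but even at 0.9 the rate is nearly three times 5%.

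**Step 5. After the change.** One pre-specified outcome has a 5% error rate. Holm's procedure on five items starts by comparing the smallest p-value with 0.05/5 = 0.01. When no item truly differs, its chance of any false finding is therefore the last column, at or below 5%.

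**The case against.** The strongest objection is that section 6.1 does not say that each item has its own test. It speaks of a proportion showing behaviour change, and Table 4 lists that as one measure. The plural *tests* might refer to the two target populations. If so, one composite tested in each population would give 1 − 0.95^2 = 9.75%, not 22.6%. This stands as a caution: item-by-item testing is the natural reading, because no rule combines the items, but it is an inference. It does not remove the need for the change, since under the other reading the composite is undefined.

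Four stronger readings are tempting and are not supported:

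- A reader might take 23% as the chance of falsely confirming the prediction. A significant item favouring the usual messages could not be presented as support, so the relevant figure is about 12%.
- A reader might take 23% as a ceiling. It is the value under independence; the strict bound is 25%.
- A reader might add the two medication items and quote a larger error rate. Table 4 keeps medication adherence apart, and the chi-square sentence names only behaviour change, so the plan does not define a family of seven.
- A reader might call this the trial's only measure of behaviour after a real alert. The 4-week questionnaire also asks, in general terms, how often participants acted on forecasts, and it asks about stopping exercise because of alerts.

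It is also fair to say that question 3 arises only if a real alert occurs.

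**Conclusion.** The concern holds. A primary question has five possible outcomes and no rule for deciding among them. This is more than a missing detail, because following the plan as written allows one item significant at 5% to support a primary claim.

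If each item is tested at 5%, the chance of at least one false difference is about 23% under independence and roughly 14–22% for latent correlations from 0.9 down to 0.3. A false finding in the predicted direction has a chance of about 12% under independence, nearly five times the 2.5% of a single test.

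These figures rest on separate item tests, a two-sided 0.05 for each, answers reduced to two categories and, in the simulation, the assumed yes rate and arm sizes. The absence of a named outcome and of a multiplicity rule rests on none of these. The plan should be changed before the data are analysed.

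**What to change.** In section 6.1:

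- Name one primary outcome for question 3. One workable choice is a yes to at least one of the five behaviours after the first real moderate alert, with *not sure* counted as no. A count of yes answers or one named behaviour would also control the error rate; what matters is that the choice is fixed in advance.
- Report the risk difference between arms with a 95% CI, alongside the chi-square test.
- State the denominator as responders to the alert questionnaire, and add a sensitivity analysis that counts non-responders as no.
- Test the five items as secondary outcomes with Holm adjustment. If no composite is wanted, make the five Holm-adjusted items the decision rule for question 3.

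This takes a few sentences and no new data. The cost is a stricter threshold for single items, 0.01 for the smallest p-value, and so less power for each. The composite does not show which behaviour changed; the secondary item results would have to supply that. Fixing the first moderate alert leaves later alerts to descriptive reporting.

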5.4.2 Recruitment and study procedure

All CityAir application users will be sent a notification about the current study containing a link to the participant information sheet. If eligible and happy to take part in the study, then they will be redirected to an online survey, using a well-known online platform (<https://www.surveymonkey.co.uk/>).

Once potential participants had agreed to take part, they will be asked to indicate whether they had a pre-existing health condition. Based on their answers, they will be divided into two groups (general public and at risk respondents). Respondents in both groups will be randomised via an algorithm run by CityAir to either a control or intervention condition.

Participants will be asked to read the scenario of a hypothetical high pollution episode and to indicate their intentions to follow the health advice given (i.e. baseline adherence intentions measure). After completion of the first questionnaire, all participants will be able to receive real-time CityAir notifications about real air pollution episodes. Whilst the control group will receive air quality notification and associated health advice in the usual UK AQI format, the intervention group will receive health advice in an alternative format (see Materials).

5.5 MATERIALS:

Table 2 shows the health advice accompanying air quality alerts in both the usual and alternative format (i.e. targeting message specificity). Table 3 shows some of the additional messages that will be sent to the intervention group and targeting specific psychosocial factors identified in our previous systematic review. Readability scores were calculated for all messages (using a readability tool available at: <https://www.webpagefx.com/tools/read-able/check.php>) and reported in Tables 2-3. To reduce the likelihood of confounding effects, the alternative messages have a similar word count and identical readability scores of 8 (i.e. they should be easily understood by 13 to 14 years old).

SHORT TITLE/ACRONYM: Improving the health impact of air quality alerts v.3

Table 2 The health advice associated with the current UK AQI compared with the alternative/more detailed health messages developed for this study.

Level of pollution	Usual messages of UK AQI*		Alternative messages (targeting message specificity)	
	General public	At risk	General public	At risk

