5.6 MEASURES

Table 4. Summary of measures.

Timing	Measure	How it will be measured
First Online Questionnaire – After reading hypothetical high air pollution scenario	Baseline intentions ^a to adopt protective behaviours in response to hypothetical, high air pollution alert	Assuming the situation described was happening right now, how much would you agree with the following statements? 
 - I intend to follow the recommendations received with the air alert to reduce exposure to air pollution - I will avoid going outdoors - I intend to reduce length or level of my physical activity outdoors - I intend to change my travel route - I intend to change my exercise location - I intend to change the time when I travel - I intend to change the time when I exercise outdoors
	Baseline medication adherence intentions ^a	If you have lung problems: 
 - I intend to use my preventer inhaler daily - I intend to carry my reliever inhaler with me
	Other baseline intention ^a (not advised behaviours)	
 - I will wear a mask as a protection from air pollution - I intend to reduce length or level of my physical exercise indoors
	Previous protective behaviour ^b	- In the past 4 weeks, how often have you taken action to reduce exposure to air pollution, I response to hearing or reading an air quality forecast?
	Planning	
 - In the last 4 weeks, to reduce your exposure to air pollution, have you considered making permanent changes to your daily travel route or exercise place and time?^c - In the last 4 weeks, how often have you checked air quality information before doing physical activity outdoors?^b
	Physical activity ^d	- To stay healthy, the NHS recommends at least 150 minutes of moderate physical activity (e.g. cycling, fast walking, swimming) every week (e.g. 30 minutes 5 days a week). Based on this, how physically active were you in the last week?
	Symptoms ^c	- Have you ever experienced symptoms caused by air pollution?
Air Alert period – Online questionnaires	Alert recall ^e	- Recently we sent you an air quality alert about poor air quality. What was the level of air pollution reported?

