Medication adherence intentions ^a	If you have lung problems: - I intend to use my preventer inhaler daily - I intend to carry my reliever inhaler with me
Other intentions (not advised behaviours) ^a	- I will wear a mask as a protection from air pollution - I intend to reduce length or level of my physical exercise indoors

Notes: ^a Measured on 9-point scales, where 1=strongly disagree to 9=strongly agree; ^b From 1 Not at all to 9 all of the time; ^c Possible answers: yes, no, not sure; ^d From 1 Not at all, to 7 more than 150 minutes; ^e Possible answers: Low, Moderate, High, Very High, Not sure, I did not receive any alert; ^f From 1=not at all likely to 9=extremely likely; ^g on a 5-point scale; ^h 1= not clear at all to 9= extremely clear. Demographic data will be collected for all the participants in the first questionnaire.

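### Primary question 3 is tested with an unadjusted chi-square, although a closely related baseline rating is collected; adjusting would help modestly, provided that rating is taken before the advice is shown

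*Combined protocol and SAP*

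**What the plan says.** Section 4 lists three primary questions. The third reads "In case of a real alert being issued during the study period, how do the different messages affect actual behaviour change". Its only between-arm analysis is in section 6.1: "Chi square tests will be performed to analyse differences in proportion of self-reported actual behaviour change between groups", for a real moderate episode. No covariate, stratum or adjusted sensitivity analysis is named.

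The outcome (Table 4, section 5.6) is a set of five behaviour items in the alert-period questionnaire. Each is answered on the scale "Possible answers: yes, no, not sure".

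The first questionnaire in Table 4 contains an item on previous protective behaviour: "In the past 4 weeks, how often have you taken action to reduce exposure to air pollution", in response to a forecast, rated 1 to 9 and not restricted to any subgroup. It also has planning items, one of which asks "have you considered making permanent changes to your daily travel route or exercise place and time".

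Elsewhere, section 6.1 adjusts the intentions outcomes for their baseline values, and the sample size in section 5.3 assumes one covariate for the main outcome measures.

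On timing, section 5.4.2 first divides participants by health status and then says "Respondents in both groups will be randomised via an algorithm run by CityAir to either a control or intervention condition". Reading the scenario is described after that. Table 4 heads the whole first-questionnaire block "First Online Questionnaire – After reading hypothetical high air pollution scenario".

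**The concern.** The baseline item and the question 3 outcome both concern acting on air quality information, one before the study and one during it. If they are correlated, a comparison that ignores the baseline item has a larger standard error than it needs. For a primary question, that is power given away at no saving.

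The second issue is who is analysed. Question 3 can be assessed only in people who answer an alert-period questionnaire. That subset forms after randomisation, and the plan gives no analysis set or missing-data method for it. If the responding arms differ in earlier behaviour, by chance or because response differs by arm, a chi-square carries that difference into the estimated message effect.

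**Working it through.** **1. The plan's own figure.** Section 5.3 states 80% power, alpha 0.05, f = 0.02, one covariate and n = 240 after 20% inflation. An ANCOVA calculation with the noncentral F distribution (1 numerator df, noncentrality f² × N) gives:
- f = 0.02 as printed: N = 19,625 before inflation, so 240 does not reproduce.
- f = 0.20: N = 199, and 199 × 1.2 = 239, which matches 240.

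I therefore use f = 0.20 (Cohen's h = 0.40 for two equal arms). Before inflation, 240 / 1.2 = 200 participants. The printed f is a separate matter.

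**2. Assumptions for question 3.** The plan gives no planning rate. I take 36% in the control arm, the median in the protocol's own review (section 1.1.5) for reducing or rescheduling outdoor activity. For h = 0.40 the other arm is then 55.8%, since 2·arcsin√0.558 − 2·arcsin√0.36 = 1.687 − 1.287 = 0.400. Allocation 1:1 and a two-sided 0.05 test are assumed. Responder counts of 200 and 100 are illustrative.

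**3. Approximate power with adjustment.** With r the within-arm correlation between baseline rating and outcome, z = 0.40 / √(4(1 − r²)/n) and power = Φ(z − 1.96).
- n = 200, r = 0: z = 0.40 / 0.1414 = 2.83, power 80.7%.
- n = 200, r = 0.5: z = 2.83 / √0.75 = 3.27, power 90.4%.

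| r | n = 200 | n = 100 |
|---|---|---|
| 0 | 80.7% | 51.6% |
| 0.2 | 82.3% | 53.2% |
| 0.3 | 84.3% | 55.4% |
| 0.4 | 87.0% | 58.8% |
| 0.5 | 90.4% | 63.7% |

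**4. Simulation of the actual tests.** Chi-square against logistic regression on arm plus a 1 to 9 baseline score. Set-up A: 36% v 55.8%, 2,500 runs, likelihood-ratio test. Set-up B: 36% v 56%, 1,500 runs, Wald test.

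| Set-up, r | n = 200: chi-square → adjusted | n = 100: chi-square → adjusted |
|---|---|---|
| A, 0.19 | gain of 1 point or less | gain of 1 point or less |
| B, 0.21 | 82.5% → 82.1% | 54.0% → 53.8% |
| B, 0.33 | 83.9% → 85.3% | 52.9% → 54.1% |
| A, 0.39 | 83.1% → 87.2% | 51.8% → 57.6% |
| A, 0.51 | 81.9% → 91.6% | 53.0% → 64.5% |
| B, 0.51 | 82.9% → 92.8% | 54.3% → 65.3% |

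The simulated gain falls short of the formula at low and middle correlations. Gains of about 1 point are close to simulation error: √(0.83 × 0.17 / 1,500) is about 1 point.

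With no true effect, rejection rates were 3.7% to 5.9% in A. In B they were 4.2% to 5.5% for the chi-square and 4.1% to 5.4% adjusted. These runs assume responders are comparable between arms.

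In B, the variance of the adjusted difference in proportions relative to the unadjusted one was 1.00 to 1.03 at r = 0, so little is lost if the item predicts nothing. At r near 0.5 it was 0.72 to 0.75.

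**5. Imbalance among responders.** With no true effect and a 0.3 SD arm difference in the baseline rating, the unadjusted difference in proportions moves by about 3, 5 and 7 percentage points at r of about 0.2, 0.33 and 0.5. The standard error of a chance imbalance is √(4/n) SD, which is 0.20 at n = 100 and 0.14 at n = 200. So 0.3 SD is 1.5 standard errors with 100 responders and about 2.1 with 200. Chance alone could plausibly produce it in the smaller set and seldom in the larger.

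**The case against.** The strongest objection concerns the covariate. The baseline intention ratings are unsuitable here because they are given after allocation in response to the advice. As documented, the previous-behaviour item sits in the same place: after randomisation and under the heading that follows the scenario. The final questionnaire has participants read the scenario and tailored advice again, which suggests the advice was also shown the first time. Messages cannot change what people did in the preceding four weeks, but they can change how it is recalled and rated. This objection stands, and it determines the fix.

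The second objection is that the correlation may be low. The item covers any forecast in the past four weeks, so it depends partly on what was forecast. Section 5.4.1 says the general public did not usually receive moderate alerts, and the chi-square concerns a moderate episode. Table 1 does not list past behaviour among the predictors of adherence. The 36% may also be too high, because general-public controls are told to carry on as normal at moderate levels. All this stands as uncertainty about the size of the gain, and nothing in the documents settles it.

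A reader might infer that the planned test is invalid. It is not: under randomisation the chi-square keeps its type I error. A reader might also infer that adjusting repairs selective response. It removes only the part of the imbalance that this item captures.

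**Conclusion.** The point holds as a matter of efficiency and limited bias protection. Primary question 3 has an unadjusted test while a closely related rating is collected from everyone. The power gain is negligible at a correlation of 0.2 or below, about 1 to 6 points at 0.33 to 0.4, and about 10 points at 0.5. These figures rest on a 36% control rate, a difference of about 20 points, and 100 to 200 responders. The correlation is not in the documents, so a definite loss of power cannot be claimed. The benefit against imbalance depends on the same correlation and on how unlike the responding arms turn out to be. The change is worth making because it costs little and loses almost nothing if the correlation is zero, but only if the rating is protected from the advice.

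**What to change.** 1. In the online form, place the *Previous protective behaviour* item before randomisation, or at least before the scenario and advice appear.
2. In section 6.1, make the main question 3 analysis a logistic regression of the alert-period behaviour outcome on arm and that 1 to 9 score. State whether it applies to each item or to a pre-defined composite, and fix the coding of not-sure answers in advance.
3. Report the covariate-standardised difference in proportions with a 95% CI, and keep the chi-square as a sensitivity analysis.
4. If the item cannot be moved, state that it is rated after allocation, keep the chi-square as the main analysis and treat the adjusted result as the sensitivity analysis.
5. Do not use the baseline intention ratings as the covariate for this question.
6. Say separately how non-response to the alert questionnaire will be handled, since this change does not settle it.

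The cost is a few sentences in section 6.1 and a change of item order, with no new participants or questions. The downside is that the odds ratio becomes conditional on the covariate, which is why the standardised difference must be reported.
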